8.2.5 Other Disease-Specific Assessments

- EULAR/ACR 2019 Classification Criteria (Screening Only) [3]
- SELENA-SLEDAI Flare Index and Thanou Modified Flare Index [4]
- Assessment of Primary Endpoint (Stage 2) and Disease and SLE Treatment Status (Stage 3)
- SF-36 (Patient- Reported) [90]
- Tender and Swollen Joint Count Assessment

Table 8.1. Stage 1 & 2 Schedule of Events

	STAGE 1 (up to 4 weeks)	STAGE 2 (up to 52 weeks)													End of Study		
		STG2-1	STG2-2	STG2-3	STG2-4	STG2-5	STG2-6	STG2-7	STG2-8	STG2-9	STG2-10	STG2-11	STG2-12	STG2-13			
Visit Number	SCRN	STG2-1	STG2-2	STG2-3	STG2-4	STG2-5	STG2-6	STG2-7	STG2-8	STG2-9	STG2-10	STG2-11	STG2-12	STG2-13	Early Termination	Unscheduled	Safety Follow Up ^L
Description	Screening	Randomization	Week 4	Week 8	Week 12	Week 16	Week 20	Week 24 ^P	Week 28	Week 32	Week 36	Week 40	Week 44	Week 48			
Visit Window	-28 Days	Day 0 ± 24 hours	± 5 days	± 5 days	± 5 days	± 5 days	± 5 days	± 5 days	± 5 days	Early Termination	Unscheduled	Safety Follow Up ^L					
Blood Draw Volumes^O																	
Clinical Draw (mL)	29	11	11	11	19	11	11	19	11	11	11	11	11	19	19	19	19
Research Draw (mL)	50	49	49	49	49	49	49	49	49	49	49	49	49	50	49	49	49
Visit Draw Total (mL)	79	60	60	60	60	60	60	60	60	60	60	60	60	69	68	68	68
General Assessments																	
Informed Consent	X																
Stage 1 Inclusion/Exclusion Criteria Assessment	X	X															
Inclusion Criteria Prior to Randomization		X															
Evaluation of Entry Packet by Adjudication Committee	X																
Withdrawal of Lupus Treatment ^{A, B}	X ^L																
Demographics	X																
Medical History	X																
Comprehensive Physical Exam ^K	X	X	X	X	X	X	X	X	X	X	X	X	X	X	X	X	X
Vital Signs	X	X	X	X	X	X	X	X	X	X	X	X	X	X	X	X	X
ECG	X														X ^C		
Adverse Event Collection	X	X	X	X	X	X	X	X	X	X	X	X	X	X	X	X	X
Concomitant Medications	X	X	X	X	X	X	X	X	X	X	X	X	X	X	X	X	X

	STAGE 1 (up to 4 weeks)	STAGE 2 (up to 52 weeks)														End of Study
		SCRN	STG2-2	STG2-3	STG2-4	STG2-5	STG2-6	STG2-7	STG2-8	STG2-9	STG2-10	STG2-11	STG2-12	STG2-13	Early Termination	Unscheduled
Visit Number	SCRN	STG2-1														
Description	Screening	Randomization	Week 4	Week 8	Week 12	Week 16	Week 20	Week 24 ^P	Week 28	Week 32	Week 36	Week 40	Week 44	Week 48		
Visit Window	-28 Days	Day 0 ± 24 hours	± 5 days	± 5 days	± 5 days	± 5 days	± 5 days	± 5 days	± 5 days	Early Termination	Unscheduled					
Disease-Specific Assessments																
EULAR/ACR 2019 Criteria for SLE	X															
PGA	X	X	X	X	X	X	X	X	X	X	X	X	X	X	X	X
BILAG 2004	X	X	X	X	X	X	X	X	X	X	X	X	X	X	X	X
Hybrid SLEDAI	X	X	X	X	X	X	X	X	X	X	X	X	X	X	X	X
SELENA-SLEDAI Flare Index and Thanou Modified Flare Index	X	X	X	X	X	X	X	X	X	X	X	X	X	X	X	X
LFA-REAL-CLINRO™	X	X	X	X	X	X	X	X	X	X	X	X	X	X	X	X
CGI-I (CGI-C & CGI-S)	X	X	X	X	X	X	X	X	X	X	X	X	X	X	X	X
Assessment of Primary Endpoint ^F			X ^D							X ^{D,E,F}						
Disease and SLE Treatment Status										X ^E	X	X ^{D,E,F}				
Tender and Swollen Joint Count Assessment	X	X	X	X	X	X	X	X	X	X	X	X	X	X	X	X
Participant Reported Outcomes^Q																
SF-36	X	X	X	X	X	X	X	X	X	X	X	X	X	X	X	X
PGI-I (PGI-C & PGI-S)	X	X	X	X	X	X	X	X	X	X	X	X	X	X	X	X
LFA-REAL-PRO™	X	X	X	X	X	X	X	X	X	X	X	X	X	X	X	X
Local Laboratory Assessments^B																
Urine Pregnancy ^G		X	X	X	X	X	X	X	X	X	X	X	X	X	X	X
SARS-CoV-2 Antigen Testing	X ^R	X												X ^M		
TB Testing (Quantiferon Gold) ^H	X															

	STAGE 1 (up to 4 weeks)	STAGE 2 (up to 52 weeks)													End of Study
Visit Number	SCRN	STG2-1	STG2-2	STG2-3	STG2-4	STG2-5	STG2-6	STG2-7	STG2-8	STG2-9	STG2-10	STG2-11	STG2-12	STG2-13	
Description	Screening	Random- ization	Week 4	Week 8	Week 12	Week 16	Week 20	Week 24 ^P	Week 28	Week 32	Week 36	Week 40	Week 44	Week 48	
Visit Window	-28 Days	Day 0 ± 24 hours	± 5 days	± 5 days	± 5 days	± 5 days	± 5 days	± 5 days	± 5 days	Early Termination Unscheduled					
Central Laboratory Assessments^B															
Hematology (CBC with differential)	X	X	X	X	X	X	X	X	X	X	X	X	X	X	X
Blood Chemistry	X	X	X	X	X	X	X	X	X	X	X	X	X	X	X
Lipids (triglycerides and cholesterol)	X														X X ^c X
Urinalysis (dipstick, microscopic, spot protein-creatinine)	X	X	X	X	X	X	X	X	X	X	X	X	X	X	X
TBNK Trucount	X ^s														
Serum Pregnancy ^G	X														
Anti-dsDNA, C3, C4	X	X	X	X	X	X	X	X	X	X	X	X	X	X	X
Immunoglobulin G	X				X			X							X X X ^c X
Autoantibodies (ANA, ENA Panel, Anticardiolipin)	X				X			X							X X X ^c X
HIV Testing	X														
Hepatitis B Surface Antigen and Core Antibody Screening (with viral load if indicated)	X														
Hepatitis C Antibody (with viral load if indicated)	X														
Mechanistic Assessments^B															
Whole Blood/PBMC/Plasma	X	X	X	X	X	X	X	X	X	X	X	X	X	X	X
Serum	X	X	X	X	X	X	X	X	X	X	X	X	X	X	X

	STAGE 1 (up to 4 weeks)	STAGE 2 (up to 52 weeks)													End of Study		
		SCRN	STG2-1	STG2-2	STG2-3	STG2-4	STG2-5	STG2-6	STG2-7	STG2-8	STG2-9	STG2-10	STG2-11	STG2-12	STG2-13		
Visit Number	SCRN																
Description	Screening	Randomization	Week 4	Week 8	Week 12	Week 16	Week 20	Week 24 ^P	Week 28	Week 32	Week 36	Week 40	Week 44	Week 48			
Visit Window	-28 Days	Day 0 ± 24 hours	± 5 days	± 5 days	± 5 days	± 5 days	± 5 days	± 5 days	± 5 days		Early Termination	Unscheduled					
Mechanistic Assessments (continued) ^B																	
RNA Assays	X	X	X	X	X	X	X	X	X	X	X	X	X	X	X	X	X
DxTegrity Blood Draw: RNA for Inflammation and Interferon Markers (for Group Stratification)	X								X							X	
Urine	X	X	X	X	X	X	X	X	X	X	X	X	X	X	X	X	X
Study Treatment / Investigational Agent																	
Long-acting Corticosteroid IM Injection	X ^I								X ^C								
Randomization to Stage 2 MMF/Placebo MMF		X															
Dispense MMF/ Placebo MMF ^J		X	X ^N	X	X	X	X	X	X								
Perform Drug Accountability			X	X	X	X	X	X	X	X	X	X	X	X	X	X	X
Treatment Survey															X		X

A. See section 3.1.1 *Stage 1: Treatment Withdrawal*, for details regarding medication withdrawal guidelines.

B. Mechanistic specimens, along with central and local lab specimens, should be collected after the participant sees the study physician and primary endpoint is assessed, but prior to initiating any changes in the participant's lupus medication including lupus treatment withdrawal in Stage 1, the administration of a corticosteroid injection, or stopping study-provided medication/beginning new or increased lupus medications during the course of the study.

C. Treatment/test to be administered if clinically indicated.

D. If at any scheduled or unscheduled visit at any time up to and including the Week 24 Visit during Stage 2 the participant is assessed as a Stage 2 treatment failure, as defined in Protocol Section 3.5.1, *Treatment Failure*, then the participant will proceed in the study as outlined in Section 3.1.2, *Stage 2 Randomization*.

E. If at any scheduled or unscheduled visit at any time after Week 24 Visit during Stage 2 the participant is assessed as a Stage 2 treatment failure, as defined in Protocol Section 3.5.1, *Treatment Failure*, then the participant will proceed in the study as outlined in Section 3.1.2, *Stage 2 Randomization*.

F. If at any scheduled or unscheduled visit a participant is assessed as a Stage 2 treatment failure, as defined in Protocol Section 3.5.1, *Treatment Failure*, coordinators will indicate treatment failure on source and in EDC.

G. Pregnancy tests for women of child-bearing potential only. First date of last period will also need to be collected.

H. To confirm the participant does not meet Exclusion criterion number 24, they need a negative Quantiferon Gold (or equivalent) assay. See Section 4.3, *Exclusion Criteria 24* for details regarding TB retest.

I. During Stage 1, participants will receive a corticosteroid injection which may be repeated if needed to achieve amelioration of symptoms. A total of 3 injections may be given up to and including the day of Stage 2 Randomization, prior to Stage 2 dosing. Dose will be dependent on the available formulation.

J. Study-provided medication will not be dispensed if participant is assessed as a Stage 2 treatment failure. The participant will either proceed to Stage 3 or will discontinue study-provided medication.

K. Physical examinations are to include, at least, the following systems: general appearance, skin, head/eyes/ears/nose/neck/throat, respiratory/chest, cardiovascular, abdominal, neurological, & musculoskeletal/extremities. Neurological exam may only be performed based on participant complaint after the screening and Stage 2 Randomization visit.

L. Participants who withdraw from their lupus medications and then screen fail prior to Stage 2 will have a safety follow-up visit 4 weeks \pm 10 days after the date of screen fail.

M. Local SARS-CoV-2 antigen testing should be performed if clinically indicated.

N. MMF/Placebo MMF will not be dispensed if the participant has stopped Stage 2 study-provided medication and has started a new or increased lupus medication due to a treatment failure.

O. Lab volumes to not exceed 550 cc over 8 weeks.

P. Participants who exit the study at Stage 2 Week 24 should complete all End of Study/Safety Follow-Up visit assessments at this time.

Q. Patient-reported outcomes should be completed in a quiet space and prior to any other study assessments.

R. Local SARS-CoV-2 antigen testing must be completed 2 days before the randomization visit. Participants will be required to self-test 2 days prior to the randomization visit and provide proof of negativity.

S. For participants who have used B cell depleting therapy within 1 year of screening, CD19+ B Cells will also be evaluated at the Screening Visit.

Table 8.2. Stage 3 Schedule of Events.

Visit Number	STAGE 3									End of Study	
	STG3-1	STG3-2	STG3-3	STG3-4	STG3-5	STG3-6	STG3-7	STG3-8	Early Termination	Unscheduled	Safety Follow Up
	Description	Re-randomization	Week 2	Week 4	Week 8	Week 12	Week 16	Week 20			
Visit Window	Day of Stage 2 Treatment Failure +5 Days ^N	± 5 days	± 5 days	± 5 days	± 5 days	± 5 days	± 5 days	± 5 days	Early Termination	Unscheduled	Safety Follow Up
Blood Draw Volumes^L											
Clinical Blood Draw (mL)	4 ^K	4	11	11	19	11	11	19	19	19	19
Research Blood Draw (mL)	1 ^K	0	49	49	49	49	49	50	49	49	49
Visit Draw Total (mL)	5 ^K	4	60	60	60	60	60	69	68	68	68
General Assessments											
Comprehensive Physical Exam ^I			X	X	X	X	X	X	X	X	X
Vital Signs		X	X	X	X	X	X	X	X	X	X
ECG						X ^A					
Adverse Event Collection		X	X	X	X	X	X	X	X	X	X
Concomitant Medications		X	X	X	X	X	X	X	X	X	X
Disease-Specific Assessments											
PGA			X	X	X	X	X	X	X	X	X
BILAG 2004			X	X	X	X	X	X	X	X	X
Hybrid SLEDAI			X	X	X	X	X	X	X	X	X
SELENA-SLEDAI Flare Index and Thanou Modified Flare Index			X	X	X	X	X	X	X	X	X
LFA-REAL-CLINRO™			X	X	X	X	X	X	X	X	X
CGI-I (CGI-C & CGI-S)			X	X	X	X	X	X	X	X	X
Disease and SLE Treatment Status ^B			X	X	X	X	X	X	X	X	X
Tender and Swollen Joint Count Assessment			X	X	X	X	X	X	X	X	X
Participant Reported Outcomes^M											
SF-36			X	X	X	X	X	X	X	X	X
PGI-I (PGI-C & PGI-S)			X	X	X	X	X	X	X	X	X
LFA-REAL-PRO™			X	X	X	X	X	X	X	X	X
Local Laboratory Assessments^C											
Urine Pregnancy ^D			X	X	X	X	X	X	X	X	X
SARS-CoV-2 Molecular Testing						X ^I					

	STAGE 3									End of Study
	STG3-1	STG3-2	STG3-3	STG3-4	STG3-5	STG3-6	STG3-7	STG3-8	Early Termination	
Visit Number										
Description	Re-randomization	Week 2	Week 4	Week 8	Week 12	Week 16	Week 20	Week 24		
Visit Window	Day of Stage 2 Treatment Failure +5 Days	± 5 days	± 5 days	± 5 days	± 5 days	± 5 days	± 5 days	± 5 days	Early Termination	Unscheduled
Central Laboratory Assessments ^C										
Hematology (CBC with differential)			X	X	X	X	X	X	X	X
Blood Chemistry		X ^H	X	X	X	X	X	X	X	X
Lipids (triglycerides and cholesterol)									X	X ^A
Urinalysis (dipstick, microscopic, spot protein-creatinine)			X	X	X	X	X	X	X	X
Anti-dsDNA, C3, C4			X	X	X	X	X	X	X	X
Immunoglobulin G	X ^K				X			X	X	X ^A
Autoantibodies (ANA, ENA Panel, Anticardiolipin)					X			X	X	X ^A
Mechanistic Assessments ^C										
Whole Blood/PBMC/Plasma			X	X	X	X	X	X	X	X
Serum			X	X	X	X	X	X	X	X
DxTeryt Blood Draw: RNA for Inflammation and Interferon Markers (for Group Stratification) ^L	X ^K							X		
RNA Assays			X	X	X	X	X	X	X	X
Urine			X	X	X	X	X	X	X	X
Study Treatment / Investigational Agent										
Long-acting Corticosteroid IM Injection		X ^E						X ^A		
Randomization to Stage 3 MMF+Voclosporin/MMF+Placebo voclosporin	X									
Dispense MMF+Voclosporin/MMF+Placebo voclosporin ^{F,G}	X		X	X	X	X	X			
Perform Drug Accountability			X	X	X	X	X	X	X	X
Treatment Survey									X	X

A. Treatment/test should be administered if clinically indicated.

B. If at any scheduled or unscheduled Stage 3 visit the participant is assessed as a Stage 3 treatment failure, then the participant will proceed in the study as outlined in Protocol Section 3.1.3: Stage 3 Re-Randomization.

C. Mechanistic specimens, along with central and local lab specimens, should be collected after the participant sees the study physician and primary endpoint is assessed, but prior to initiating any changes in the participants lupus medication including lupus treatment withdrawal at screening, the administration of a corticosteroid injection, or stopping study-provided medication/beginning new or increased lupus medications during the course of the study.

D. Pregnancy tests for women of child-bearing potential only. First date of last period will also need to be collected.

E. An additional corticosteroid injection may be given up to 2 weeks after re-randomization whether or not it was given at time of Stage 2 treatment failure as well for a total of 2 corticosteroid injections from the time of Stage 2 Treatment Failure up to and including the Stage 3 Week 2 Visit.

F. MMF 1000mg BID+Voclosporin (23.7 BID) or MMF 1000mg BID+Placebo voclosporin. Participants who previously received placebo MMF in stage 2 will receive a two-week taper-up of MMF.

G. Study-provided medication will not be dispensed if participant receives a corticosteroid injection or has started new or increased lupus medications. The participant will stop Stage 3 study drug.

H. Creatinine for eGFR only

I. Physical examinations are to include, at least, the following systems: general appearance, skin, head/eyes/ears/nose/neck/throat, respiratory/chest, cardiovascular, abdominal, neurological, & musculoskeletal/extremities Neurological exam may only be performed based on patient complaint.

J. Local SARS-CoV-2 molecular testing (or alternative viral test per institutional standard) should be performed if clinically indicated.

K. If not already collected as a part of the Stage 2 Visit.

L. Lab volumes to not exceed 550 cc over 8 weeks.

M. Patient-reported outcomes should be completed in a quiet space and prior to any other study assessments.

N. The re-randomization visit should be completed on the date that treatment failure is identified + 5 days.

9 Mechanistic Assays

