3.1.2 Stage 2: Randomization

One hundred and twenty qualifying participants who withdraw from treatment as described in protocol Section 3.1.1, *Stage 1: Treatment Withdrawal*, and meet improvement criteria for randomization as outlined in Section 4.2.2, *Inclusion criteria required prior to randomization*, will be randomized (1:1) to receive up to 48 weeks of either MMF or corresponding MMF placebo. For the first 2 weeks, a scheduled “taper-up” of MMF will take place. Participants will receive 500 mg MMF (or corresponding MMF placebo) BID for 7 days, followed by 500mg and 1,000mg MMF (or corresponding MMF placebo) in divided doses for 7 days. They will then continue at a stable dose of 1,000mg MMF (or corresponding MMF placebo) BID. Visits to evaluate AEs, vital signs, hematology and chemistry, study medication compliance, medication use, disease status, participant reported outcomes, and to obtain biomarker samples will occur every 4 weeks after randomization.

Participants will be followed for a maximum of 48 weeks on study-provided medication in Stage 2. If a participant experiences an increase in SLE symptoms at any scheduled or unscheduled visit at or before the Stage 2 Week 24 visit, they will proceed in the study as follows:

- If the participant is deemed a Stage 2 treatment failure as defined in protocol Section 3.2, *Primary Endpoint*, and a corticosteroid injection is deemed sufficient for treatment without new or increased lupus medication, then a blood sample for mechanistic studies will be drawn, the injection will be administered, and the participant will immediately proceed to Stage 3: Re-randomization. (See Section 3.1.3, *Stage 3 Re-Randomization*).
- If the participant is deemed a Stage 2 treatment failure as defined in protocol Section 3.2, *Primary Endpoint*, and a corticosteroid injection is deemed sufficient for treatment without new or increased lupus medication, but the participant refuses the corticosteroid injection, then a blood sample for mechanistic studies will be drawn, and the participant will still immediately proceed to Stage 3: Re-randomization without the corticosteroid injection. (See Section 3.1.3, *Stage 3: Re-Randomization*).

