3.5 Definitions

3.5.1 Treatment Failure

Treatment failure is defined as the first occurrence after randomization (Stage 2) or as the first occurrence after re-randomization (Stage 3) of any of the following events:

- Corticosteroid injections or treatment with a new or increased lupus medication, except the occasional use of corticosteroids for reasons not associated with SLE flare (see Section 7.1.2.2, *Prednisone (or equivalent)* for additional information); or
- BILAG flare, defined as any item marked new or worse that could support a BILAG A (severe flare) or 2 organs with items marked new or worse that could support a BILAG B (moderate flare), and if the participant's condition is deemed by the investigator to be "moderately worse" or "much worse" compared to the day of randomization, as assessed by the CGI-C; or
- Premature permanent discontinuation of study-assigned treatment for any reason.

For Stage 2, the reference values for the CGI-C should be the investigator's determination of the participant's condition at the Stage 2 Day 0 Randomization Visit. For Stage 3, the reference values for the CGI-C should be the investigator's determination of the participant's condition at the most recent assessment before the Stage 3 Re-randomization Visit.

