7.1.2.2 Prednisone (or equivalent)

Individuals may screen for the study if taking up to 20 mg/day prednisone (or equivalent) but both the participant and the investigator must be willing and able to taper to 10 mg/day (under cover of long-acting corticosteroids) by the Stage 2 Randomization Visit. Prednisone (or equivalent) may be continued at a stable dose \leq 10 mg/day once the participant is randomized into the trial. Individuals are not eligible for the study if they have taken \geq 40 mg/day of prednisone within 4 weeks prior to the Screening Visit.

To accommodate the occasional use of extra corticosteroids for reasons not associated with SLE flares, increases of up to 40 mg/day that are decreased back to the baseline dose within 14 days are permitted, but not on more than one occasion prior to Week 20 in Stage 2 and one occasion prior to Week 20 in Stage 3.

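### Section 3.5.1 and Table 8.2 note G treat the permitted early Stage 3 corticosteroid injection as a failure and a reason to stop drug; Sections 3.1.3 and 7.1.1 say it is neither

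*Combined protocol and SAP*

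**What the plan says.** **Text that permits the injection.** The synopsis and Section 3.1.3 allow a single long-acting IM corticosteroid injection in the first 2 weeks of Stage 3, as late as the Week 2 Visit, to relieve symptoms. They state that it does not count as a Stage 3 failure and does not oblige anyone to stop Stage 3 drug. Section 7.1.1 repeats this. Note E to Table 8.2 permits it too, allowing "a total of 2 corticosteroid injections from the time of Stage 2 Treatment Failure up to and including the Stage 3 Week 2 Visit".

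**Text that counts it as a failure.** Section 3.5.1 defines Stage 3 failure as the first listed event after re-randomization. The first item is "Corticosteroid injections or treatment with a new or increased lupus medication, except the occasional use of corticosteroids for reasons not associated with SLE flare". The section it cites for that exception, 7.1.2.2, concerns "the occasional use of extra corticosteroids for reasons not associated with SLE flares". Section 3.3.1 defines the Stage 3 failure endpoint by the criteria in 3.5.1 and does not mention 3.1.3.

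**Text that stops drug.** Note G to Table 8.2 reads "Study-provided medication will not be dispensed if participant receives a corticosteroid injection or has started new or increased lupus medications", followed by "The participant will stop Stage 3 study drug". It exempts neither the injection that note E allows nor the one given at Stage 2 failure.

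**Related text.** Item 7 of Section 6.5 repeats the injection wording without the exception, but its lead-in is permissive and it depends on 3.5.1. Under note B, anyone assessed as a Stage 3 failure is handled so that "the participant will proceed in the study as outlined in Protocol Section 3.1.3: Stage 3 Re-Randomization". Section 3.1.3 holds the exception, but it also stops drug in anyone deemed a Stage 3 failure.

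**The concern.** The same injection has opposite consequences depending on which section is followed.

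- **Coding.** An analyst working from 3.3.1 and 3.5.1 records a failure in a participant whom 3.1.3 regards as still failure-free. This affects the cumulative incidence of Stage 3 failure and the time to Stage 3 failure.
- **Conduct.** A site working from note G stops drug in a participant whom 3.1.3 keeps on treatment. The stop then meets the third criterion of 3.5.1, "Premature permanent discontinuation of study-assigned treatment for any reason". If the injection is later recoded as permitted, the stop remains a failure and the lost exposure is not recovered.
- **Week 24 BICLA.** A participant moved onto the failure pathway may leave before Week 24. BICLA at that visit is a secondary endpoint, and Section 13.4.6 uses it to define response in the Stage 3 mechanistic analyses.

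**Working it through.** **1. Does the exception in 3.5.1 cover the injection?** The exception needs a reason unrelated to a lupus flare, and 7.1.2.2 describes temporary dose increases of up to 40 mg/day that return to baseline within 14 days. The early Stage 3 injection is given to relieve lupus symptoms just after a Stage 2 failure, so it is not covered. Section 3.1.3 says the injection does not meet a definition that, as written, it does meet.

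**2. Can note G be right as written?** Note G is attached to the row that dispenses drug, which includes the re-randomization visit. Under Section 3.1.2, after a qualifying Stage 2 failure, "the injection will be administered, and the participant will immediately proceed to Stage 3: Re-randomization". Section 3.6 stratifies re-randomization by whether that injection was given. Read literally, note G would refuse drug to participants whom the design expects to enrol in Stage 3, so its wording is too broad.

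**3. Timing, from the documents.**
- Latest permitted injection: Week 2 = Day 14, visit window +5 days, so Day 19.
- Week 24 = Day 168.
- Final visit after a Stage 3 failure (3.1.3): 4 weeks ± 10 days after the last dose. For a stop on Day 19, the latest date is 19 + 28 + 10 = Day 57.
- Gap to Week 24: 168 − 57 = 111 days. Week 24 BICLA is missed unless the participant stays in the study as Section 6.5 encourages.

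**4. The plan's own Stage 3 numbers (Section 13.7).**
- Expected entrants: 60 × 0.80 = 48 from placebo and 60 × 0.60 = 36 from MMF, total 84.
- Expected responders among the 24 placebo-then-MMF participants: 24 × 0.35 = 8.4 to 24 × 0.50 = 12, matching the stated 8–12.

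**5. Illustrative head-counts.** The documents give no injection rate, so the injected share *s* is assumed. The failure-free rate *f* of 35–50% is stated for the placebo-then-MMF cell only and is applied here to all 84. Every permitted injection is assumed to be handled under 3.5.1 or note G.

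- Earlier failure dates: 84 × *s*.
- Changed Week 24 status, if injection is independent of later outcome: 84 × *s* × *f*.
- Changed Week 24 status, if injected participants are half as likely to stay failure-free (assumed, overall *f* kept): 84 × *s* × 0.5*f* / (1 − 0.5*s*).

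| Assumed share *s* | Earlier failure dates | Status changed, independent | Status changed, half as likely |
|---|---|---|---|
| 10% | 84 × 0.10 = 8.4 | 8.4 × 0.35 = 2.9 to 8.4 × 0.50 = 4.2 | 8.4 × 0.175 / 0.95 = 1.5 to 8.4 × 0.25 / 0.95 = 2.2 |
| 5% (low end) | 84 × 0.05 = 4.2 | from 4.2 × 0.35 = 1.5 | not computed |
| 50% (high end) | 84 × 0.50 = 42 | up to 42 × 0.50 = 21 | not computed |

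Within the placebo-then-MMF cell, under independence, the 8.4–12 expected responders become 24 × 0.35 × 0.9 = 7.6 to 24 × 0.50 × 0.9 = 10.8 at a 10% share.

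**The case against.** The best defence is that the specific rule overrides the general one. The synopsis, 3.1.3 and 7.1.1 all address the failure definition directly, note E permits the injection, and note B sends failures back to 3.1.3. The intent is clear, and a careful reader would reach it. That stands as evidence of intent. It does not settle the text: no order of precedence is stated, 3.3.1 cites 3.5.1 alone, and neither 3.5.1 nor note G points to the exception. Note G is itself a specific, mandatory, Stage 3-only instruction.

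A second argument is that the dispensing row is blank at Week 2, so note G may have been meant only for later injections. This narrows the clash at the Week 2 Visit itself. But the sentence ordering a stop has no time limit, and the bar on dispensing still applies at Week 4 to someone injected earlier.

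It is also fair that reading note G as a bar at re-randomization cannot be intended, given the stratification in 3.6 and the reference to stopping drug already begun. That confirms the wording needs correcting.

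Day 19 depends on using the visit window. If the limit of two weeks is taken strictly, the date is Day 14 and the latest exit is 14 + 28 + 10 = Day 52, still well before Week 24.

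Finally, the head-counts rest on assumed rates and on every injection being mishandled, and Stage 3 is exploratory. Both points are accepted: the counts show scale only, and they limit how serious this is.

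**Conclusion.** The inconsistency is real. Section 3.1.3 shows what was intended; 3.5.1 and note G, followed as written, produce wrong Stage 3 failure coding and wrong drug stops, and the stops cannot be repaired at analysis.

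The effect is confined to Stage 3: the two failure endpoints, drug exposure and, through wrong stops, Week 24 BICLA. These are secondary endpoints whose inference Section 13.4.5 labels supportive. The Stage 2 primary endpoint and sample size are unaffected, and no bias between arms is claimed. The firm figures are the dates: a failure recorded by Day 19 and a possible exit by Day 57, against Day 168. The number of participants affected is unknown, since over assumed shares of 5–50% the range is too wide to be a forecast. With only about 18 to 24 expected per Stage 3 cell, however, a few wrong stops would be noticeable. The correction should be made.

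**What to change.** 1. **Section 3.5.1, first criterion.** Add an exception: *except, in Stage 3, the single long-acting IM corticosteroid injection permitted no later than the Stage 3 Week 2 Visit (Sections 3.1.3 and 7.1.1)*. Refer to it in Section 6.5 item 7.
2. **Table 8.2 note G.** Reword: *Do not dispense study medication, and stop Stage 3 study drug, if the participant starts or increases a lupus drug or has any corticosteroid injection other than (i) the one given at Stage 2 failure or (ii) the one note E permits by the Stage 3 Week 2 Visit.*

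Sections 3.3.1 and 13.4.5 then inherit the corrected definition, and 3.1.3 and 7.1.1 stay as they are. The cost is one clause, one cross-reference and one footnote, with no new data and no change to the sample size.
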